6.3 Missing Data Imputation

No data will be imputed for any efficacy or safety analyses except for the PRO questionnaires, for analyses of the HCV RNA endpoints, and for analysis of the persistence of resistance. If a respondent answers at least 50% of the items in a multi-item scale of the SF-36v2, the missing items will be imputed with the average score of the answered items in the same scale. In cases where the respondent did not answer at least 50% of the items, the score for that domain will be considered missing. Similarly, the missing items of the FACIT-F questionnaire will be imputed with the average score of the answered items in the same scale as long as more than 50% (≥ 7 out of 13) of the items in the scale are answered. The SF-36v2 Mental and Physical Component Summary measures will not be computed if any domain is missing.

HCV RNA values will be selected for an SVR analysis based on visit windows as defined in Section 6.2. When there is no HCV RNA value in a visit window based on defined visit windows, the closest values before and after the window, regardless of the value chosen for the subsequent and preceding window, will be used for the flanking imputation described below.

If a subject has a missing HCV RNA value at a post-Day 1 visit but with undetectable or unquantifiable HCV RNA levels at both the preceding value and succeeding value, the HCV RNA level will be considered undetectable or unquantifiable, respectively, at this visit for this subject. In addition, if a subject has an unquantifiable HCV RNA level at the preceding value and an undetectable HCV RNA level at the succeeding value, or vice versa, the HCV RNA level will be imputed as unquantifiable at this visit for this subject. For SVR analyses, if there is no value in the appropriate window after flanking imputation but there is an HCV RNA value after the window, then it will be imputed into the SVR window. Subsequent to this flanking and backward imputation, if a subject is missing a value for the visit window associated with the analysis, the subject will be imputed as a visit failure (i.e., not undetectable or unquantifiable).

If a subject starts another treatment for HCV, then all HCV RNA and PRO assessment values for this subject measured on or after the start date of the new HCV treatment will be excluded from analyses. The subject will be considered a failure for summaries of viral response at all time points after the start of the new HCV treatment.

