Breakthrough = confirmed HCV RNA \geq LLOQ after HCV RNA < LLOQ during treatment, or confirmed increase from nadir in HCV RNA (two consecutive HCV RNA measurements > 1 log₁₀ IU/mL above nadir) at any time point during treatment. A single breakthrough value (\geq LLOQ or > 1 log₁₀ IU/mL above nadir) followed by lost to follow-up will be considered a breakthrough (i.e., will not require confirmation).

On-treatment virologic failure = breakthrough or failure to suppress during treatment (all on-treatment values of HCV RNA \geq LLOQ) with at least 6 weeks (defined as study drug duration \geq 36 days) of treatment.

RVR (rapid virologic response) = HCV RNA < LLOQ in the Week 4 window.

EOTR (end of treatment response) = HCV RNA < LLOQ in the Week 12 window for subjects receiving 12 weeks of treatment and in the Week 24 window for subjects receiving 24 weeks of treatment.

SVR₄ = HCV RNA < LLOQ in the SVR₄ window (4 weeks after the last actual dose of study drug) without any confirmed quantifiable (\geq LLOQ) post-treatment value during that SVR window.

SVR₁₂ = HCV RNA < LLOQ in the SVR₁₂ window (12 weeks after the last actual dose of study drug) without any confirmed quantifiable (\geq LLOQ) post-treatment value before or during that SVR window.

SVR₂₄ = HCV RNA < LLOQ in the SVR₂₄ window (24 weeks after the last actual dose of study drug) without any confirmed quantifiable (\geq LLOQ) post-treatment value before or during that SVR window.

Relapse₁₂ = confirmed HCV RNA \geq LLOQ between end of treatment and 12 weeks after last actual dose of active study drug (up to and including the SVR₁₂ assessment time point) for a subject with HCV RNA < LLOQ at Final Treatment Visit who completes treatment.

Relapse₂₄ = confirmed HCV RNA \geq LLOQ during SVR₂₄ window among subjects who achieved SVR₁₂ and have data available during the SVR₂₄ window.

Relapse_{late} = confirmed HCV RNA \geq LLOQ at any time after the SVR₂₄ assessment time point for a subject who achieved SVR₂₄ and has post-SVR₂₄ HCV RNA data available.

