Relapse_{overall} = confirmed HCV RNA \geq LLOQ between end of treatment and up to and including the last HCV RNA measurement collected in the PT Period for a subject with HCV RNA < LLOQ at Final Treatment Visit who completes treatment. For relapse analyses, the completion of treatment is defined as a study drug duration \geq 77 days for subjects assigned to 12 weeks of treatment and \geq 154 days for subjects assigned to 24 weeks of treatment. If the last available post treatment value is \geq LLOQ, then the subject will be considered a relapse (i.e., will not require confirmation). Relapse analyses will exclude subjects who do not have any post-treatment HCV RNA values.

HCV re-infection is defined as confirmed HCV RNA \geq LLOQ after the end of treatment in a subject who had HCV RNA < LLOQ at Final Treatment Visit, along with the post-treatment detection of a different HCV genotype, subtype, or clade compared with baseline, as determined by phylogenetic analysis of the NS3 or NS5A, and/or NS5B gene sequences. Re-infection in the case of the same HCV subtype is defined as a clade

switch, as indicated by the lack of clustering between the baseline and post-treatment sequences by phylogenetic analysis. If phylogenetic analysis is not possible due to technical difficulties, HCV re-infection may be determined with a confirmed HCV genotype or subgenotype switch by the Versant HCV Genotype Inno-LiPA Assay v2.0 or Sanger assay.

Any subjects with documented re-infection will be excluded from relapse analyses and will be analyzed separately.

Reasons for SVR₁₂ Non-Response

Subjects who do not achieve SVR₁₂ (SVR₁₂ non-responders) will be categorized as having:

1. On-treatment virologic failure (see **On-treatment virologic failure** definition);
2. Relapse (defined according to the **Relapse₁₂** definition for subjects who complete treatment);
3. Prematurely discontinued study drug with no on-treatment virologic failure (defined as any SVR₁₂ non-responder who prematurely discontinued study drug (duration < 77 days for subjects assigned to 12 weeks of treatment or duration < 154 days for subjects assigned to 24 weeks of treatment) and did not meet the **On-treatment virologic failure** definition);
4. Missing follow-up data in the SVR₁₂ window [defined as any subject who completed study drug without data in the SVR₁₂ window and not meeting the definitions of (1), (2), or (3)];

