5. Other (including subjects with documented re-infections and subjects defined as any SVR₁₂ non-responder not meeting the definitions of [1] – [4], such as a subject with a single quantifiable value within the SVR₁₂ window followed by an undetectable value beyond the SVR₁₂ window).

Reasons for SVR₂₄ Non-Response

Subjects who do not achieve SVR₂₄ (SVR₂₄ non-responders) will be categorized as having:

1. On-treatment virologic failure (see **On-treatment virologic failure definition**);
2. Relapse (defined according to the **Relapse₁₂** definition for subjects who complete treatment);
3. Relapsed after achieving SVR₁₂ (see **Relapse₂₄**);
4. Prematurely discontinued study drug with no on-treatment virologic failure (defined as any SVR₂₄ non-responder who prematurely discontinued study drug and did not meet the **On-treatment virologic failure**, **Relapse₁₂**, or **Relapse₂₄** definitions);
5. Missing follow-up data in the SVR₂₄ window [defined as any subject who completed study drug without data in the SVR₂₄ window, and not meeting the definitions of (1), (2), (3), or (4)];
6. Other (including subjects with documented re-infections and subjects defined as any SVR₂₄ non-responder not meeting the definitions of [1] – [5]).

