10.7 Additional Efficacy Analyses

The following additional HCV RNA efficacy endpoints will be summarized and analyzed on the ITT-I population, as specified:

- The number and percentage of subjects with on-treatment virologic failure;
- The number and percentage of subjects with post-treatment relapse;
- The number and percentage of subjects with documented re-infection;
- The number and percentage of subjects with RVR;
- The number and percentage of subject with EOTR;
- The number and percentage with unquantifiable HCV RNA at each post-baseline visit throughout the Treatment Period (using data from the central laboratory as observed, i.e., no imputation for missing data);
- The number and percentage of subjects with HCV RNA < LLOQ 24 weeks after the last actual dose of study drug (SVR₂₄);
- Reasons for not achieving SVR₂₄ for subjects who do not;
- Mean change from baseline in prothrombin time (PT), International normalized ratio (INR), FibroTest, and albumin to each applicable post-baseline time point;
- The number of subjects who fail to suppress and accompanying listing;
- The number of subjects who breakthrough any time during treatment and accompanying listing;
- The number of completers with final on-treatment HCV RNA < LLOQ who relapse within the SVR₄ window, SVR₁₂ window, or SVR₂₄ window and accompanying listing;
- The concordance between SVR₁₂ and SVR₂₄ will be assessed.

In the above analyses that use the number and percentage of responders, 2-sided 95% Wilson score confidence interval for a binomial proportion will be calculated.

Imputations for missing data will be performed as described in Section 6.3 for analyses of SVR, RVR, and EOTR, where a missing response will be imputed as a failure after performing the described imputation. All other endpoints will be presented using data as observed. For the change from baseline to each post-baseline time point in PT/INR, Fibrotest, and albumin, descriptive statistics will be calculated.

The number and percent of subjects who fail to suppress HCV RNA and received at least 6 weeks of treatment (active study drug duration ≥ 36 days) will be tabulated along with the subject numbers corresponding to the subjects who failed to suppress.

The number of subjects who breakthrough at any time during treatment and within each protocol-specified visit (defined in Table 2) will be summarized along with a corresponding listing displaying the subject numbers at the first occurrence of breakthrough.

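### SAP 10.1 leaves some relapses after SVR12 in neither Relapse24 nor Relapse-late, and lists those subjects as missing for SVR24

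*SAP*

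**What the plan says.** SAP 10.1 splits relapse after SVR12 into two categories. Relapse24 is confirmed HCV RNA at or above LLOQ in the SVR24 window, "among subjects who achieved SVR₁₂ and have data available during the SVR₂₄ window". Relapse-late is confirmed viraemia after that time point, "for a subject who achieved SVR₂₄ and has post-SVR₂₄ HCV RNA data available". A third measure, Relapse-overall, runs from the end of treatment "up to and including the last HCV RNA measurement collected in the PT Period", for completers who were below LLOQ at the Final Treatment Visit. It requires neither SVR24 nor a sample in the SVR24 window. A last available post-treatment value at or above LLOQ counts as relapse without confirmation. Documented re-infections are excluded.

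SAP Table 3 sets the SVR24 window at days 127 to 210 but the PT Week 24 visit window at days 127 to 266.

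SAP 6.3 fills an empty SVR window in two steps. Flanking comes first, for a subject "with undetectable or unquantifiable HCV RNA levels at both the preceding value and succeeding value". If the window is still empty "but there is an HCV RNA value after the window, then it will be imputed into the SVR window". SAP 10.7 confines imputation to SVR, RVR and EOTR, and adds: "All other endpoints will be presented using data as observed".

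Among the reasons for SVR24 non-response in SAP 10.1, reason 3 points to Relapse24 only. Reason 5 (missing follow-up) is "defined as any subject who completed study drug without data in the SVR₂₄ window" who meets none of reasons 1 to 4.

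**The concern.** The two relapse categories do not cover all relapses after SVR12. One needs an observed sample in an 84-day window and the other needs SVR24 to have been achieved. A subject whose first sample after the window is quantifiable can fail both tests, and then documented viraemia is reported as missing follow-up.

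No missed visit is needed. A PT Week 24 sample drawn on days 211 to 266 is valid for its visit but lies outside the SVR24 window.

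The omission runs in one direction. For the same visit timing, a subject below LLOQ is granted SVR24 and joins the Relapse-late denominator, while a viraemic subject drops out of both categories. At stake are the completeness of Relapse24 and Relapse-late and the correctness of the planned summary of reasons for not achieving SVR24. The same subject would be a relapse in one table and missing in another.

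**Working it through.** The documents give no figure to reproduce, because this concerns classification rules. The rules were applied as written to sample patterns. Every subject below is a completer with SVR12, below LLOQ at the Final Treatment Visit and without documented re-infection. Plus means at or above LLOQ and minus means below LLOQ. Relapse is judged on observed data, as SAP 10.7 states.

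| Samples after the SVR12 window | SVR24 (route) | Relapse24 | Relapse-late | Relapse-overall | SVR24 reason |
|---|---|---|---|---|---|
| Day 364 plus, day 728 plus | No (carried back) | No | No | Yes | 5, missing |
| Day 364 plus, last value | No (carried back) | No | No | Yes | 5, missing |
| Day 230 plus, day 364 plus | No (carried back) | No | No | Yes | 5, missing |
| Day 364 minus, day 728 plus, day 1092 plus | Yes (flanking) | No | Yes | Yes | none |
| Day 168 plus, day 364 plus | No (observed) | Yes | No | Yes | 3, Relapse24 |
| Day 168 minus, day 364 plus | Yes (observed) | No | Yes | Yes | none |

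The first three rows are the gap. Flanking fails because the succeeding value is quantifiable. The carried-back value then makes the subject an SVR24 non-responder, which rules out Relapse-late. With no observed value on days 127 to 210, Relapse24 is not met, reason 3 does not apply, and reason 5 is what remains.

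The fourth row shows the limit of the gap: if the first sample after day 210 is below LLOQ, flanking grants SVR24 and later viraemia is Relapse-late. The last two rows show that subjects sampled inside the window are classified correctly.

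For the asymmetry, compare the third row with a subject whose day 230 sample is below LLOQ. The values before and after the empty window are then both below LLOQ, flanking grants SVR24, and the subject is eligible for Relapse-late.

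Non-completers with the first three patterns go to reason 4 (premature discontinuation), not reason 5. Documented re-infections go to the residual category.

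**Size.** The planning assumption of 4% without SVR12 and the planned 1650 subjects give 0.96 × 1650 = 1584 subjects with SVR12. Two rates must be assumed, since the documents give neither: 0.5% to 1% relapsing after SVR12, and 5% to 10% with no sample on days 127 to 210.

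- Relapses after SVR12: 1584 × 0.005 = 7.9, to 1584 × 0.01 = 15.8.
- In the gap, if missing the window is unrelated to relapse: 7.9 × 0.05 = 0.4, to 15.8 × 0.10 = 1.6.

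Under independence this overstates the count, because it includes relapses preceded by a negative sample after the window, which are classified correctly. It would be too low if relapsing subjects attend less regularly.

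**The case against.** The strongest reply is that the carried-back value itself fills the window. SAP 6.3 imputes it there, so it might count as available data. The subject would then be Relapse24 under reason 3 if the imputed value is accepted as confirmed, or would go to the residual category if not. The SAP never says whether an imputed value counts for Relapse24 or reason 5, and one could argue that the reasons list belongs to the SVR24 analysis, where imputation applies. This has some force, but it does not rescue the text. It conflicts with the observed-data rule in SAP 10.7, and it would date viraemia first seen on day 364 or later to a window that closes on day 210. One reading labels a relapse as missing; the other misdates it.

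A second reply is that reason 5 refers to missing data in the SVR24 window, which is literally true of these subjects. That is so, but the summary would still give missing data as the explanation for a failure whose cause is on record.

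Four stronger readings are tempting, and the documents do not support them.

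- A reader might infer that every SVR12 subject without a window sample who later becomes viraemic is lost. Only those whose first later sample is quantifiable are affected.
- A reader might infer that these relapses vanish from the report. Relapse-overall counts them, and so does the SAP 10.7 table of relapses by window, which has rows for relapse after the SVR24 window and at any time post-treatment. SAP 10.7 names no separate Relapse-late table, so its explicitly planned tabulation of late relapse is not biased.
- A reader might infer that a study objective is compromised. Five-year durability of virologic response is not a stated objective. The objectives are clinical outcomes by SVR12 status, FibroScan change and the SVR12 percentage; SVR24 and relapse sit among the additional analyses.
- A reader might infer that the primary comparison is affected. SVR12 status does not depend on these rules.

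**Conclusion.** The concern holds in a narrow form. It requires SVR12, completed treatment, no observed sample on days 127 to 210, a quantifiable first sample afterwards (confirmed or last available) and no documented re-infection. On the observed-data rule, such a subject belongs to neither Relapse24 nor Relapse-late and is reported as missing for SVR24, while other planned outputs count a relapse. Failures are left out selectively, because the same timing with a value below LLOQ earns SVR24.

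The effect is small. Under the assumed rates, about 0 to 2 subjects are involved, and one subject in 1584 is 0.06 percentage points. Relapses after SVR12 would themselves be few on those assumptions (about 8 to 16), so one or two could still be visible in a late-relapse rate. The SVR24 rate does not move, since the subject is a failure under either reading. The defect is worth correcting because it can be shown from the text and costs little to remove.

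**What to change.** Amend SAP 10.1 as follows.

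1. Define relapse after SVR12 as HCV RNA at or above LLOQ, confirmed or as the last available value, at any time after the SVR12 window in any subject with SVR12 and at least one later observed value. Keep the re-infection exclusion. Do not newly restrict the definition to completers: reason 4 for SVR24 non-response already allows for premature discontinuers who meet Relapse24.
2. Classify by the day of first observed detection: Relapse24 if on or before day 210, Relapse-late if after day 210. Do not require SVR24.
3. State that relapse and its timing use observed values only, not values carried back under SAP 6.3.
4. Widen SVR24 non-response reason 3 to any relapse after SVR12 where no value below LLOQ established SVR24. Keep reason 5 for subjects with no quantifiable value after the window. A single unconfirmed quantifiable value that is later contradicted would fall to the residual category.

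The cost is SAP wording and minor programming, with no new data. There are two downsides: the late relapse rate may be slightly higher, and a relapse first seen after day 210 may have begun earlier. Listing the last negative and first positive day for each such subject would make the second point visible.

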10.0 Efficacy Analysis

10.1 General Considerations

The primary efficacy analysis on clinical outcomes will be performed on all subjects in the ITT population as defined in Section 5.1. All other efficacy analyses will be performed on the ITT-I population.

Treatment effects will be evaluated based on a two-sided significance level of 0.05 (when rounded to three decimal places). The data from the ITT-I population will be presented in one column/row as it represents the labelled treatment.

Plasma HCV RNA levels will be determined for each sample collected by the central laboratory using the COBAS[®] AmpliPrep/COBAS[®] TaqMan[®] HCV Test, v2.0. For this assay, the lower limit of quantification (LLOQ) and the lower limit of detection (LLOD) is 15 IU/mL. HCV RNA results that are detectable but not quantifiable are reported as "< 15 IU/mL" and results that are not detectable are reported as "NON-DETECTED."

Assessment of Clinical Outcomes

Incidence of the following clinical outcome events will be collected during the 12/24 weeks of treatment and the 5-year (PT Week 260) Post-Treatment Period. Data will be adjudicated by an independent outcome committee and results will be reported in the "Clinical Outcome" eCRFs:

- All-cause death: Death due to any cause.
- Liver-related death: Death as the result of a liver-related cause.
- Liver decompensation: Development of any of the following conditions: ascites, hepatic encephalopathy, or variceal bleeding.
- Liver transplantation: any subject who had a liver transplantation.

- Hepatocellular carcinoma (HCC): development of HCC in any subject at any time during the study. HCC is defined by histologic confirmation or a > 1 cm mass lesion on cross-sectional imaging that meets the diagnostic criteria for HCC according to EASL guidelines.
- Composite of any of the above outcomes.

Definitions for HCV RNA Efficacy Endpoints

Note that a confirmed quantifiable post-treatment value is defined as two consecutive post-treatment HCV RNA measurements \geq LLOQ. During treatment, a confirmed quantifiable value is defined as any two consecutive HCV RNA values \geq LLOQ, either both during treatment or at the final treatment measurement and the next consecutive post-treatment measurement.

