10.8 Resistance Analyses

If possible, subjects treated with study drug who experience virologic failure will have resistance testing conducted if 1) they have on-treatment breakthrough; 2) if they have post-treatment relapse, with a study drug duration ≥ 77 days for subjects assigned to 12 weeks of treatment or with a study drug duration ≥ 154 days for subjects assigned to 24 weeks of treatment; or 3) if they have at least 6 weeks of treatment and fail to suppress by Week 6 (i.e., meet virologic stopping criteria). Subjects meeting one of these criteria will be referred to as subjects in the primary virologic failure (PVF) population, and a listing by subject that includes HCV subtype, IL28B genotype, reason for non-response, time point(s) sequenced as closest to time of VF, and HCV RNA value at the VF time point(s) will be produced for these subjects. In addition, all listings described below will display HCV subtype and reason for non-response in the subject identifier for each subject. A separate listing will delineate all subjects in the PVF population for whom no sequencing was performed (e.g., lost to follow-up while HCV RNA ≤ 1000 IU/mL).

Only samples with an HCV RNA level of ≥ 1000 IU/mL will undergo sequence analysis in order to allow accurate assessment of products of amplification. Therefore if the HCV RNA level at the time of virologic failure (VF) is < 1000 IU/mL, the sample closest in time after the failure with an HCV RNA level ≥ 1000 IU/mL will be used if available.

The regions of interest for next generation sequencing (NGS) from all evaluated time points in this study are those encoding full length NS3/4A, NS5A, and NS5B. The prototypic reference sequences used for analysis will be H77 for genotype 1a or Con1 for genotype 1b.

For each DAA target, resistance-associated amino acid variants will be identified by AbbVie Clinical Virology. Amino acid positions where resistance associated variants have been identified in vitro and/or in vivo are 1) for ABT-450: 36, 43, 55, 56, 80, 155,

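### SAP 10.1 waives confirmation for relapse but not for re-infection, so a completer whose only viraemic post-treatment sample is the last one is counted as a relapse even if it sequences as a different virus

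*SAP*

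**What the plan says.** All the definitions are in SAP 10.1, under the HCV RNA efficacy endpoints.

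- **Confirmation.** After treatment, "a confirmed quantifiable post-treatment value is defined as two consecutive post-treatment HCV RNA measurements" at or above LLOQ.
- **Re-infection.** "HCV re-infection is defined as confirmed HCV RNA" at or above LLOQ in a subject who was below LLOQ at the Final Treatment Visit, "along with the post-treatment detection of a different HCV genotype, subtype, or clade compared with baseline". If phylogenetic analysis fails for technical reasons, "HCV re-infection may be determined with a confirmed HCV genotype or subgenotype switch" on another assay. That fallback changes how the switch of virus is shown. It does not lift the RNA condition.
- **Relapse.** The subject must have completed treatment and been below LLOQ at the Final Treatment Visit. The paragraph on Relapse_overall adds that, when the last available post-treatment value is at or above LLOQ, "then the subject will be considered a relapse (i.e., will not require confirmation").
- **Precedence.** "Any subjects with documented re-infection will be excluded from relapse analyses". The SAP gives no separate meaning to *documented*, so the re-infection definition has to supply it.

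Two other rules matter. Under SAP 6.3, HCV RNA values "measured on or after the start date of the new HCV treatment will be" dropped, so a single viraemic value before retreatment can become the last available one. Under SAP 10.8, only samples with at least "1000 IU/mL will undergo sequence analysis".

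**The concern.** The SAP asks for more RNA evidence before it accepts re-infection than before it accepts relapse, and relapse is the default when the evidence falls short. A last sample that is viraemic and carries a different strain is direct evidence against relapse of the baseline virus, yet the rules file it as relapse.

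Three planned outputs are at stake:

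- The relapse and re-infection tables in SAP 10.7 would be wrong in opposite directions. If both counts are small, a few subjects matter.
- SAP 10.8 places post-treatment relapses in the primary virologic failure (PVF) population. It treats a variant below 2% at baseline and at 2% or more later as post-baseline, and hence as treatment-emergent. Ordinary differences between two strains would then be tabulated as emergent resistance and could enter the persistence summaries.
- For early cases, if the last-value rule also applies to Relapse12 and Relapse24, the SVR12 and SVR24 non-response categories change. So does the mITT-I-GT+VF population of SAP 10.6, which keeps relapses as failures but drops non-responders in the *Other* category, where documented re-infections are placed.

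**Working it through.** **Step 1: apply the rules.** The plan states no figure on this point to reproduce. Take a treatment completer who was below LLOQ at the Final Treatment Visit.

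| Post-treatment pattern | Virus | RNA confirmed? | Label under SAP 10.1 |
|---|---|---|---|
| Only the last sample viraemic | same as baseline | no | relapse, by the last-value rule |
| Only the last sample viraemic | different | no | **relapse**: re-infection is not met, so the subject is not excluded |
| Last two consecutive samples viraemic | different | yes | re-infection, excluded from relapse |
| One viraemic sample, then a last value below LLOQ | either | no | neither |

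The second row is the defect. Nothing in SAP 10.6 to 10.8 corrects it, and the protocol does not define re-infection.

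**Step 2: where it can occur.** It can occur at Post-Treatment (PT) Week 260, at a post-treatment discontinuation visit, at loss to follow-up, or when retreatment starts before a second sample. Protocol Table 7 schedules both HCV RNA and resistance samples at PT Week 260 and at post-treatment discontinuation, so a sequenceable last sample with no successor is part of the design.

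**Step 3: share of re-infections left with one viraemic sample.** The visits are PT Weeks 4, 12, 24, 52, 104, 156, 208 and 260 (protocol Table 7), so the intervals are 4, 8, 12, 28, 52, 52, 52 and 52 weeks. Assume constant re-infection risk over 260 weeks and scheduled samples only.

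- *No dropout.* First seen at PT Week 260: (260 − 208)/260 = 52/260 = 20%.
- *20% dropout.* The 20% is the upper figure in SAP 4.3. Assume uniform dropout times and no sample at dropout. Among dropouts, the chance that the re-infection is first seen at the last attended visit is the sum of products of adjacent intervals over 260²: (4×8 + 8×12 + 12×28 + 28×52 + 3×52×52)/67,600 = 10,032/67,600 = 0.1484. The chance that it is seen at all is the sum of each interval times the time of the visit before it, over 260²: 27,888/67,600 = 0.4125. The share is (0.8×0.20 + 0.2×0.1484)/(0.8 + 0.2×0.4125) = 0.1897/0.8825 = 21.5%.
- *In addition, half of the rest retreated before the next visit (assumed).* 0.215 + 0.785×0.5 = about 61%. This figure ignores confirmatory testing and should not be used alone.
- *Unscheduled confirmatory sample in 80% of cases (assumed).* 0.2×21.5% = 4.3%, and 0.2×61% = about 12%.

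**Step 4: scale per subject.** One relabelled subject moves a percentage based on the planned enrolment by 1/1650 = 0.06 percentage points. An absolute total cannot be computed, because the documents give no re-infection rate.

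**The case against.** The best defence is that the asymmetry is a cautious convention. The SAP relaxes confirmation for failures: breakthrough followed by loss to follow-up, and relapse on the last value. It also imputes missing SVR data as failure. Re-infection is the label that takes a subject out of the relapse analyses, so a higher standard of proof avoids favouring the drug. The SAP does not state this reasoning, however, and it does not justify counting a sequenced different strain as relapse or its strain differences as emergent resistance.

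Several limits do stand:

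- A reader might infer that any subject whose last sample is a different genotype is reported as a relapse. The text does not support that. A viraemic preceding sample confirms the RNA, and the subject is then a re-infection.
- A reader might infer that late relapse is certainly affected. The last-value rule is in the Relapse_overall paragraph, while Relapse_late has its own definition that asks for confirmation. Whether the rule extends to it is unclear.
- Protocol 5.4.3 asks for prompt confirmatory testing. The PT Week 260 window runs to Day 2002, which is 2002 − 1820 = 182 days past nominal, so a later sample can still be analysed. The discontinuation visit can also supply a second sample. These reduce the cases but do not guarantee a second value.
- The sequencing threshold does not make a second sample worthless. It serves accurate amplification, and a single discordant genotype could be a sample mix-up.
- The resistance listings show HCV subtype, so a subtype switch might be noticed by eye. The summary counts would still include the subject.

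**Conclusion.** The concern holds in a narrow form. The subject must have completed treatment, been below LLOQ at the Final Treatment Visit, and had the last available sample as the only viraemic post-treatment one. That subject is counted as a relapse, at least in overall or anytime relapse and in the PVF population, even when the sample shows a different genotype, subtype or clade.

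A reader might infer that the main results are at risk. They are not. SVR12 status does not depend on the relapse or re-infection label, so the log-rank and Cox comparisons, the FibroScan comparison by SVR12 and the SVR12 rate are unchanged. Relapse counts belong to the additional efficacy analyses in SAP 10.7.

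The number of subjects is unknown. The 20% for PT Week 260 rests on constant risk and scheduled samples only. The 4% to 12% that stay unconfirmed rests further on the assumed dropout pattern, retreatment of none or half, and 80% unscheduled confirmation. All are shares of an unknown number of re-infections. It should still be corrected, because a stated rule gives a wrong label and the correction is simple.

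**What to change.** Add to SAP 10.1: when a subject's final post-treatment HCV RNA result is at or above LLOQ and the sequence from that sample shows a genotype, subtype or clade that differs from baseline, the subject is classed as re-infected without RNA confirmation, is removed from every relapse definition and from the relapse part of the PVF population, and is flagged in the listing as unconfirmed.

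The cost is a short text change and the matching programming before database lock. It uses samples and sequences already planned. The one downside is that a sample mix-up could be labelled re-infection; the flag makes such cases visible.
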